5.2 Schedule of study assessments

For Visit 4 through Visit 6, planned clinic visits should be scheduled as indicated with a window of ± 4 days relative to Visit 3. For Visit 8 through Visit 15, planned clinic visits should be scheduled as indicated with a window of ± 7 days relative to Visit 3. From Visit 16 onward, planned clinic visits should be scheduled as indicated with a window of ± 14 days relative to Visit 3.

Table 5–1: Schedule of assessments

Visit Study Week	First Period						Second Period											
	Selection Period		Evaluation Period ^a				Maintenance Period ^b											
	V1	V2	V3	V4	V5	V6	V7	V8	V9	V10	V11	V12	V13	V14	V15	V16 ^c ...	V17 ^d ...	
	D-9 to D-2	D-2 to D0	W0	W2	W4	W6	W8	W10	W12	W14	W18	W22	W26	W32	W38	W50...	W62...	
Written informed consent	X																	
Inpatient				X		X												
Registration	X		X															
Eligibility assessment	X		X															
Medical/procedures history	X																	
Demographics	X																	
AED history	X																	
Epilepsy history	X																	
Physical examination	X																	
Neurological examination	X																	
Vital signs ^e	X		X	X	X	X	X			X	X	X	X		X	X	X	
Seizure counts ^f	X		X	X	X	X	X			X	X	X	X		X	X	X	
Laboratory safety assessment ^h	X			X	X	X				X			X		X	X	X	
LEV plasma level			X	X	X	X	X			X	X	X	X					
Body weight	X		X	X	X	X	X			X	X	X	X		X	X	X	
Height	X												X		X			
Concomitant AED(s)	X		X ^g	X	X	X	X			X	X	X	X		X	X	X	
Concomitant non-AED(s)	X		X ^g	X	X	X	X			X	X	X	X		X	X	X	

Table 5–1: Schedule of assessments

Visit Study Week	First Period						Second Period											
	Selection Period		Evaluation Period ^a				Maintenance Period ^b											
	V1	V2	V3	V4	V5	V6	V7	V8	V9	V10	V11	V12	V13	V14	V15	V16 ^c ...	V17 ^d ...	
	D-9 to D-2	D-2 to D0	W0	W2	W4	W6	W8	W10	W12	W14	W18	W22	W26	W32	W38	W50...	W62...	
Concomitant medical procedures	X		X ^g	X	X	X			X		X	X	X			X	X	X
Adverse events	X		X ^g	X	X	X			X		X	X	X			X	X	X
Dispense/return study drug			X ⁱ	X	X	X			X		X	X	X			X	X	X
Study drug compliance				X	X	X			X		X	X	X			X	X	X
ECG	X																X	
CT scan/MRI ^j	X																	
EEG ^k	X																	
IVRS/IWRS	X		X	X	X	X			X		X	X	X			X	X	X
Dispense/collect DRC	X ^l		X	X	X	X			X		X	X	X			X	X	X
Dispense subject's ID card	X																	
Fallback option ^m				X	X													
C-SSRS ⁿ																X ⁿ	X ⁿ	

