3.2.2 Schedule of Study Assessments

The study protocol gives the overall study schedule and the permissible intervals for these visits expressed as the number of days relative to Visit 3: Section 5.2 of protocol.

Subjects who were directly enrolled in the Second Period based on the protocol prior to Amendment 3 will also be included in the efficacy and safety analysis with remapping of visit numbers to correspond to the ones for subjects who enrolled in the First Period.

[Table 3–1](#) presents the assessment schedule for subjects:

- who are enrolled prior to Protocol Amendment 3 and are not 48h video-EEG failures; or
- who are enrolled according to Protocol Amendment 3; or
- who are enrolled prior to Protocol Amendment 3 and are 48h video-EEG failures

This document cannot be used to support any marketing application and any extensions or variations thereof.
PUBLIC COPY

Table 3–1: Assessment Schedule

Study Visit	Target day*	Visit Window	Week number
Subjects:			

 • who are enrolled prior to Protocol Amendment 3 and are not 48h video-EEG failures or • who are enrolled according to Protocol Amendment 3 			
Evaluation Period			
Visit 3	Day 1		Week 0
Visit 4	Day 15	Day 11 to Day 19	Week 2
Visit 5	Day 29	Day 25 to Day 33	Week 4
Visit 6	Day 43	Day 39 to Day 47	Week 6
Maintenance Period			
Visit 8	Day 71	Day 64 to Day 78	Week 10
Visit 10	Day 99	Day 92 to Day 106	Week 14
Visit 11	Day 127	Day 120 to Day 134	Week 18
Visit 12	Day 155	Day 148 to Day 162	Week 22
Visit 13	Day 183	Day 176 to Day 190	Week 26
Visit 15	Day 267	Day 260 to Day 274	Week 38
Visit 16	Day 351	Day 337 to Day 365	Week 50
Visit 17	Day 435	Day 421 to Day 449	Week 62
Every 12 weeks			
Subjects:			

 • who are enrolled prior to Protocol Amendment 3 and are 48h video-EEG failures 			
Dose Adjustment Period			
Visit 6	Day 1		Week 0
Visit 7	Day 15	Day 11 to Day 17	Week 2
Visit 8	Day 29	Day 25 to Day 33	Week 4
Visit 9	Day 43	Day 39 to Day 47	Week 6
Maintenance Period			
Visit 10	Day 57	Day 50 to Day 64	Week 8
Visit 11	Day 85	Day 78 to Day 92	Week 12
Visit 12	Day 113	Day 106 to Day 120	Week 16
Visit 13	Day 141	Day 134 to Day 148	Week 20
Visit 14	Day 183	Day 176 to Day 190	Week 26
Visit 15	Day 225	Day 221 to Day 232	Week 32
Visit 16	Day 309	Day 295 to Day 323	Week 44
Visit 17	Day 393	Day 379 to Day 407	Week 56
Every 12 weeks			

Table 3–1: Assessment Schedule

Study Visit	Target day*	Visit Window	Week number

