-------------	-------------	--------------	-------------

Note: the day of the first dose of study medication is defined as Study Day 1, while the day before the date of first dose of study medication is defined as Study Day -1 (there is no Study Day 0).

* Day relative to first study drug intake

In the event that more than 1 assessment occurs within a given visit window, the assessment closest to the target date will be used in summaries for the given visit. If 2 assessments are equally close to the target day, the latest assessment will be used.

Table 3–2 presents the mapping of Study Visits to Analysis Visits for subjects:

- who are enrolled prior to Protocol Amendment 3 and are not 48h video-EEG failures; or
- who are enrolled according to Protocol Amendment 3; or
- who are enrolled prior to Protocol Amendment 3 and are 48h video-EEG failures

Analysis visits will be used for analysis of long-term safety and efficacy data.

This document cannot be used to support any marketing authorization application and any extensions or variations thereof.
PUBLIC COPY

Table 3–2: Analysis Visit Mapping Table

Analysis Visit	Week number	Relative day since first study drug intake	Analysis window	Subjects enrolled prior to Protocol Amendment 3 and are not 48h video-EEG failures; or subjects who are enrolled according to Protocol Amendment 3	Subjects enrolled prior to Protocol Amendment 3 and are 48h video-EEG failures
Retrospective Baseline^[2]		-	2 weeks prior to Visit 1		
Baseline Period					
-1	-1	-9	-9 – 0	Visit 1 Visit 2 ^[3]	Visit 1 Visit 2 ^[3]
Evaluation/Dose Adjustment/Maintenance Period					
0 ^[4]	0	1		Visit 3	Visit 6
1	2	15	2 – 22	Visit 4	Visit 7
2	4	29	23 – 36	Visit 5	Visit 8
3	6	43	37 – 50	Visit 6	Visit 9
4	8	57	51 – 64	-	Visit 10
5	10	71	65 – 78	Visit 8 (Day 71)	-
6	12	85	79 – 95	-	Visit 11 (Day 85)
7	15	106	96 – 116	Visit 10 (Day 99)	Visit 12 (Day 113)
8	18	127	117 – 137	Visit 11 (Day 127)	-
9	21	148	138 – 158	Visit 12 (Day 155)	Visit 13 (Day 141)
10	24	169	159 – 179	-	-
11	27	190	180 – 200	Visit 13 (Day 183)	Visit 14 (Day 183)
12	30	211	201 – 231	-	Visit 15 (Day 225)
13	36	253	232 – 295	Visit 15 (Day 267)	-
14	48	337	296 – 379	Visit 16 (Day 351)	Visit 16 (Day 309)
15	60	421	380 – 463	Visit 17 (Day 435)	Visit 17 (Day 393)

16	72	505	464 – 547	Visit 18 (Day 519)	Visit 18 (Day 477)
17	84	589	548 – 631	Visit 19 (Day 603)	Visit 19 (Day 561)
Every 12 weeks					
Down-titration Period					
EDV/EOS					
Safety Follow-Up Period					
Safety Follow-Up	-	-			

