EDV= Early Discontinuation Visit; EOS= End of Study

[1] Day relative to first study drug intake

[2] Retrospective Baseline is only applicable to seizure count data. For other analyses the time window of “2 weeks prior to Visit 1” for baseline is not applied.

[3] Study Visit 2 is only applicable for those subjects enrolled prior to Protocol Amendment 3.

[4] Analysis visit 0 is not applicable to laboratory test, since Week 0 is not scheduled for them.

In the event that more than 1 assessment occurs within a given analysis visit window, the assessment closest to the target date will be used in summaries for the given visit. If 2 assessments are equally close to the target day, the latest assessment will be used.

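### SAP Table 3-2 contains two visit mappings that disagree, so some compliant Visits 10, 12 and 13 can be assigned to analysis visits with no scheduled visit, and Visits 12 and 13 can share one

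*SAP*

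**What the plan says.** Protocol 5.2 sets the tolerance for the long-term visits: "For Visit 8 through Visit 15, planned clinic visits should be scheduled as indicated with a window of" ±7 days relative to Visit 3. SAP Table 3-1 turns this into permitted day ranges. For the main cohort (everyone except the video-EEG failures enrolled before Protocol Amendment 3) these are "Day 64 to Day 78" for Visit 8, "Day 92 to Day 106" for Visit 10, "Day 148 to Day 162" for Visit 12 and "Day 176 to Day 190" for Visit 13.

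SAP Table 3-2 then defines the analysis visits. Each row has a target day and a day window, plus one column per cohort naming the study visit that belongs there. A dash means no study visit. For the main cohort AV4, AV6, AV10 and AV12 carry a dash; AV10 carries one for both cohorts.

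On use, SAP 3.2.2 states: "Analysis visits will be used for analysis of long-term safety and efficacy data". Where a window holds more than one assessment, "the assessment closest to the target date will be used in summaries for the given visit", and "If 2 assessments are equally close to the target day, the latest assessment will be used".

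**The concern.** The study-visit columns and the day windows give different answers for some visits made on time. Table 3-2 names AV7 for Visit 10, AV9 for Visit 12 and AV11 for Visit 13, but the targets for those visits (Days 99, 155 and 183) lie only three days inside an edge of the named window. A visit four to seven days off target on that side is compliant, yet lies outside the window.

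Two programmers could therefore produce different tables from the same data. Under the day windows, a compliant visit can appear in a row meant to be empty for its cohort, or be left out because another visit shares the window. The tables concerned are the combined-period seizure-frequency variables (SAP 8.2.1, 8.2.2, 8.3.2), laboratory values (10.3), vital signs (10.4.1.2), ECG (10.4.2.2) and possibly clinically significant weight (10.4.3.2). Seizure frequency is also exposed through its counting interval: SAP 8.2.1 starts the count for each AV on the day after the preceding AV, so moving or discarding a visit alters the next interval or leaves its start undefined.

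**Working it through.** **Step 1: reproduce the permitted windows.** Target day ± tolerance (±4 for Visits 4–6, ±7 for Visits 8–15, ±14 from Visit 16) gives all 11 main-cohort ranges in Table 3-1 exactly. For example, Visit 12: 155 ± 7 = Days 148–162.

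**Step 2: place every permitted day in the Table 3-2 window that contains it (main cohort).**

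| Visit | Permitted days | Named AV (window) | Days outside | AV they fall in | Share |
|---|---|---|---|---|---|
| 8 | 64–78 | AV5 (65–78) | 64 | AV4 (51–64), dash | 1/15 |
| 10 | 92–106 | AV7 (96–116) | 92–95 | AV6 (79–95), dash | 4/15 |
| 12 | 148–162 | AV9 (138–158) | 159–162 | AV10 (159–179), dash | 4/15 |
| 13 | 176–190 | AV11 (180–200) | 176–179 | AV10 (159–179), dash | 4/15 |

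Visits 4, 5, 6, 11, 15, 16 and 17 are fully contained.

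**Step 3: shared windows.** Visits 12 and 13 both fall in AV10 for 4 × 4 = 16 of 15 × 15 = 225 permitted day pairs. From target Day 169, Visit 12 on Days 159–162 is 10, 9, 8 or 7 days away, and Visit 13 on Days 176–179 is 7, 8, 9 or 10 days away. Visit 12 is strictly closer in 6 pairs, Visit 13 in 6, and 4 are ties. The later assessment wins ties, so Visit 13 is kept in 10 pairs and Visit 12 in 6. In all 16, AV9 and AV11 are empty for that subject.

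**Step 4: video-EEG failures**, using the Table 3-1 windows as printed.
- Visit 12 (106–120) is named under AV7 (96–116), but Days 117–120 fall in AV8 (117–137).
- Visit 13 (134–148) is named under AV9, but Days 134–137 also fall in AV8. AV8 has a dash for this cohort, so these two visits again share a window in 16 of 225 pairs.
- Visit 14 (176–190) is named under AV11, but Days 176–179 fall in AV10.
- Single-day spills occur at Visits 10, 11, 15, 16 and 17.

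**Step 5: how often.** The documents do not say how visits scatter within their windows, so this needs an assumption. Let q be the chance that a main-cohort visit falls on its four exposed days, equal for Visits 10, 12 and 13 and independent between visits. At least one shift has probability 1 − (1 − q)³, and Visits 12 and 13 share AV10 with probability q².

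| Assumed scatter | q | At least one shift | Visits 12 and 13 share AV10 |
|---|---|---|---|
| Uniform over 15 days | 4/15 = 26.7% | 1 − (11/15)³ = 60.6% | (4/15)² = 7.1% |
| Normal about target, SD 4 days | 17.1% | 43% | 2.9% |
| Normal about target, SD 3 days | 11.7% | 31% | 1.4% |
| Normal about target, SD 2 days | 4.0% | 12% | 0.2% |

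The normal rows are rounded to whole days and truncated at ±7.

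**Step 6: can one set of windows serve both cohorts?** AV7 would have to cover main Visit 10 (92–106) and failures' Visit 12 (106–120), hence 92–120. AV8 would cover main Visit 11, 120–134. AV9 would cover failures' Visit 13 (134–148) and main Visit 12 (148–162), hence 134–162. These overlap at Days 120 and 134, so a common set cannot contain every permitted window.

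**The case against.** The strongest defence is that assignment is nominal. SAP 3.2.2 introduces Table 3-2 as a mapping of study visits to analysis visits and speaks of renumbering visits; SAP 8.1.1 uses Study Visit 6 and Analysis Visit 3 interchangeably. On that reading no scheduled visit moves and none share a window. It is a fair reading, but the same table also states day windows, and the duplicate rule selects among assessments within a window. Under purely nominal assignment that rule would have almost nothing to act on. Each AV would hold at most one scheduled visit per subject, SAP 3.2.3 keeps unscheduled visits out of by-visit presentations unless otherwise stated, and SAP 3.2.4 already sends early-discontinuation data to a scheduled visit. The conflict remains.

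A second defence is that nearest-day assignment is a coherent way to pool two cohorts with different schedules. All 12 exposed main-cohort days at Visits 10, 12 and 13 are closer to the target of the AV they fall in than to that of their named AV. Visit 13 on Day 176, for instance, is 7 days from AV10's target (169) and 14 from AV11's (190). This stands: either rule is defensible, but the SAP has to choose one.

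Third, the consequences are limited, and this also stands. The 61% rests on uniform, independent visit days. Sharing AV10 requires Visits 12 and 13 to be 14 to 20 days apart against 28 planned, and it is rarer still if a late visit tends to be followed by a late one. Visit 12 has no laboratory sampling (Protocol 8.2.6), so a shared AV10 drops no laboratory result. Subject listings keep all data, and weight and height summary statistics are described only as by visit (SAP 10.4.3.2).

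**Conclusion.** The point holds as a conflict between two rules in one table. Read by its day windows, Table 3-2 can move compliant main-cohort Visits 10, 12 and 13 (4 of 15 permitted days each) and Visit 8 (1 of 15) into AVs with no scheduled visit. It can also drop Visit 12 or Visit 13 from the summary (16 of 225 day pairs). Video-EEG failures are exposed at Visits 12, 13 and 14. These counts follow from the tables alone; the proportion of subjects affected, from 12% to 61% in the cases shown, depends on the assumed scatter.

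A reader might infer more than the documents support:
- That on-time visits will be misplaced. They can be, on the outer four days of one side only; visits on target day map correctly, and under nominal assignment none move.
- That data are lost. An assessment is left out of a by-visit summary but stays in the listings.
- That the submission cut-off is affected. It depends on the last subject who completes the Evaluation Period reaching Visit 13 (SAP 4.3), not on AV assignment.
- That the efficacy claim is at risk. The primary analysis (AV3) and the hierarchical tests (AV1, AV2) are unaffected because the Visit 4–6 windows are contained. The effect is confined to descriptive long-term summaries.

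A correction before programming is still warranted, since the rule as written can produce two different sets of tables.

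**What to change.** State in SAP 3.2.2 that scheduled visits are assigned to analysis visits by the study-visit columns of Table 3-2, with unscheduled and early-discontinuation data handled as SAP 3.2.3 and 3.2.4 already provide. No scheduled visit then shifts or shares an AV. If day windows are preferred, define them separately for the two cohorts so that each permitted visit window lies inside one AV; Step 6 shows that a common set cannot do this.

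Under either option, SAP 8.2.1 should also say where the seizure count starts when the preceding AV is empty, because dashed rows leave that open even under nominal assignment.

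The cost is one sentence in SAP 3.2.2, a clause in 8.2.1 and a change to the visit-mapping code. No data collection changes.

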3.2.3 Unscheduled Visits

If not otherwise stated, data from unscheduled visits are:

- Not considered for by-visit presentations
- Considered for a respective period depending on the date when the unscheduled visit occurred
- Presented in subject data listings

3.2.4 Mapping of Assessments Performed at Early Discontinuation Visit

Efficacy and safety assessments at an Early Discontinuation Visit (EDV) that correspond to a scheduled visit will be summarized at the scheduled visit corresponding to the EDV if the assessment was scheduled to occur at that visit. In the event that the subject discontinues between two scheduled visits the data from the EDV are presented with data corresponding to the next scheduled visit for the subject. For subjects who had more than one EDV because of the starting dose of the Down-Titration Period, only the first EDV will be mapped to the scheduled visit.

3.2.5 Age

3.2.5.1 Chronological Age

For a given date, chronological age in months is defined as: (Date – Date of birth) / 30.4375, assuming that the date difference is given in days.

3.2.5.2 Adjusted Age

Pre-Term birth will be accounted for by using the adjusted age which is defined as

- $[(\text{Date} - \text{Date of Birth}) - (36 - \text{number of weeks pre-term}) \times 7] / 30.4375$
for subjects of chronological age < 12 months and
- Chronological age, otherwise

If not specified otherwise, adjusted age at the date of the assessment is used for all analyses.

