6.1 Inclusion criteria

To be eligible to participate in this study, all of the following criteria must be met:

- 1a. An Institutional Review Board (IRB)/Independent Ethics Committee (IEC) approved written Informed Consent form is signed and dated by the parent(s) or legal representative. Subject/legal representative/caregiver is considered reliable and capable of adhering to the protocol (eg, able to understand and complete diaries), visit schedule, or medication intake according to the judgment of the Investigator.
- 2a. Subject must have a diagnosis of epilepsy with partial onset seizures (ie, seizures of focal onset), whether or not secondarily generalized.
Subject has had an EEG and a brain computerized tomography (CT) scan or brain magnetic imaging (MRI) consistent with a diagnosis of localized epilepsy according to the International Classification of Epilepsies and Epileptic Syndromes (1989) (see Section 17.2) and consistent with partial onset seizures according to the Classification of Epileptic Seizures (1981) (see Section 17.1). If the EEG and brain CT scan and brain MRI were not performed prior to the Screening Visit (Visit 1), the assessment needs to be completed and results must be available prior to Visit 3.
3. Subject must be male or female from 1 month to <4 years of age. Pre-term infants aged <1 year are to be stratified into an appropriate age category using the best estimate of their corrected gestational age.
4. For subjects on adjunctive therapy, subject must be on a stable AED regimen (ie, a maximum of 2 AEDs) for the Selection and Evaluation Periods of the study. Minor adjustments to the

dose of current AEDs are allowed only prior to Visit 1. Monotherapy subjects must not receive AED treatment, receive temporary AED treatment, or switch an AED prior to Visit 1.

5. Subject weighs $\geq 3.0\text{kg}$.
6. Subject may have Vagal Nerve Stimulation (VNS) which has been implanted for at least 6 months prior to Visit 1; the settings must be stable for at least 2 months prior to Visit 1. Activated VNS must be counted as 1 of the 2 AEDs.

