3.2.5.3 Age at Entry Into Study

The adjusted age at entry into study is defined as the adjusted age at the screening date. This is also referred to as “Age at entry into study”

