4.8 Examination of Subgroups

In this study 4 age categories will be investigated: 1 month to <6 months, 6 months to <1 year, 1 year to <2 years, and 2 years to <4 years. For the primary efficacy variable the data of the two youngest age categories will be pooled and data of the primary efficacy variable will be summarized by the so-obtained 3 age-categories and overall.

Note: for the age classification, the age at entry into study is used (Section 3.2.5.3).

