6.5.1.3 Listings

A listing Lifestyle Status presents for subjects on adjunctive therapy and for subjects on monotherapy, separately:

- Age Category
- Site/Subject Number
- Did the Subject use alcohol within the past 6 months
- Did the Subject use illicit drugs within the past 6 months

A listing Pre-Term Birth Status presents for subjects on adjunctive therapy and for subjects on monotherapy, separately:

- Age Category
- Site/Subject Number
- Was Subject Pre-Term Infant
- If Yes, Number of Weeks Pre-Term

A listing Family Medical History presents for subjects on adjunctive therapy and for subjects on monotherapy, separately:

- Age Category
- Site/Subject Number
- System Organ Class
- Preferred Term
- Reported condition
- Start date and stop date of reported condition.

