9.1 Pharmacokinetics

9.1.1 Definitions and Derivations

For the calculation of descriptive statistics, a LEV plasma concentration below the lower limit of quantification (LLOQ) will be substituted by LLOQ/2.

Dose-normalized (to 10mg/kg for aged subjects of 6 months and above, or 7mg/kg for age less than 6 months) LEV plasma concentrations are derived as follows:

Dose-normalized LEV plasma concentrations = LEV observed plasma concentration / actual dose given (mg/kg) \times 10 (mg/kg) or 7 (mg/kg).

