12.3.1 Hematology

Table 12-1: PCST values for Hematology

Parameter	Age range	Unit (conventional)	Abnormality Criteria (conventional)	Unit	Abnormality Criteria (standard)	
Red blood cell count	<2 years	$10^{12}/L$	< 3.0	T/L	< 3.0	
	≥2 years		< 3.5		< 3.5	
Hematocrit	<2 years	%	≤ 27	%	≤ 27	
	≥2 y - <18 y		> 45		> 45	
			≤ 29		≤ 29	
			> 47		> 47	
Hemoglobin	<2 years	g/dL	≤ 9.0	g/L	≤ 90	
	≥2 y - <18 y		> 15.0		> 150	
			≤ 9.5		≤ 95	
			> 16.0		> 160	
Platelets	>1 month	$10^9/L$	≤ 100	G/L	≤ 100	
			> 600		> 600	
White blood cell count	<12 years	$10^9/L$	< 3.5	G/L	< 3.5	
			> 15.0		> 15.0	
Neutrophil count	>1 month	$10^9/L$	< 1.5	G/L	< 1.5	
Lymphocyte	<6 months	%	≤ 30.0	%	≤ 30.0	
	6 m - <6 y		≤ 22.0		≤ 22.0	
Monocyte	>1 month	%	≥ 20.0	%	≥ 20.0	
Eosinophil	>1 month	%	≥ 10.0	%	≥ 10.0	
Basophil	>1 month	%	≥ 3.0	%	≥ 3.0	
Reticulocyte			\$		\$	
MCV			\$		\$	
MCH			\$		\$	
MCHC			\$		\$	

Abbreviations: dL = deciliter; L = liter; m: month; mg = milligram; mmol = millimoles; μ mol = micromoles; U = unit; y: year

MCH=mean corpuscular hemoglobin; MCHC=mean corpuscular hemoglobin concentration; MCV=mean corpuscular volume

[§] Not presented in reference [2]

Note: The adjusted age (Section 3.2.5.2) at the assessment/visit will be used to determine within which percentile the subject is included.

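### The SAP's adjusted-age formula runs backwards when its input is read as labelled, and it is not limited to pre-term infants

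*SAP*

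**What the plan says.** SAP 3.2.5.2 (Adjusted Age) opens "Pre-Term birth will be accounted for by using the adjusted age which is defined as" and gives a two-part rule. Writing w for its input, which it calls the number of weeks pre-term:

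- chronological age under 12 months: adjusted age in months = [(date − date of birth) − (36 − w) × 7] / 30.4375;
- otherwise: chronological age.

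The first part has no condition that the infant was born early. The section adds: "If not specified otherwise, adjusted age at the date of the assessment is used for all analyses". SAP 3.2.5.3 states: "The adjusted age at entry into study is defined as the adjusted age at the screening date". SAP 4.8 notes that "for the age classification, the age at entry into study is used".

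The input appears again in the pre-term birth listing of SAP 6.5.1.3, after a yes/no item on pre-term status: "If Yes, Number of Weeks Pre-Term". Inclusion criterion 3 in Protocol 6.1 reads: "Pre-term infants aged <1 year are to be stratified into an appropriate age category using the best estimate of their corrected gestational age".

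**The concern.** A correction for prematurity should take off the number of weeks by which the infant was early. With the input as labelled, the SAP takes off 36 minus that number. An infant one week early then loses more age than an infant twelve weeks early, and the deduction is far too large in both cases.

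The scope is also too wide. The rule covers every infant under 12 months, while the protocol corrects only those born pre-term. Because the number of weeks is listed only when the pre-term item is answered yes, a term infant either has no value, so that adjusted age cannot be computed, or has a recorded 0 and loses 252 days.

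Adjusted age is the SAP's default age, so an error here spreads to:

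- age at entry and the four-category age summaries (SAP 3.2.5.3, 4.8, 6.1);
- the PK summaries by age category (SAP 9.1.2) and the normalisation reference in SAP 9.1.1, which is 10 mg/kg "for aged subjects of 6 months and above, or 7mg/kg for age less than 6 months";
- the abnormality limits, where SAP 12.3.1 says the adjusted age "at the assessment/visit will be used to determine within which percentile the subject is included", with the same note in 12.3.2, 12.5 and 12.6. The limits exposed are those with cut-points below 12 months: lymphocytes, GGT, total protein (no limit below 2 months), pulse and blood pressure at 6 months, limits stated only for over 1 month, and the weight centiles, which start at 6 months.

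**Working it through.** **Inputs.** The formula, the 12-month condition and the divisor 30.4375 come from SAP 3.2.5.1 and 3.2.5.2. The meaning of w (weeks early, recorded only for pre-term infants) comes from the label in SAP 6.5.1.3. The documents give no range for w, so 0 to 12 is an assumption. The plan gives no worked figure to reproduce.

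**Field as labelled.** One week is 7/30.4375 = 0.230 months.

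- SAP deduction: (36 − w) × 7/30.4375
- Intended deduction: w × 7/30.4375
- Computed age too low by the difference: (36 − 2w) × 7/30.4375

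| Weeks early (w) | SAP deduction | Intended deduction | Age too low by |
|---|---|---|---|
| 0 (only if a 0 is recorded) | 252 d = 8.28 months | 0 | 8.28 months |
| 1 | 245 d = 8.05 | 7 d = 0.23 | 7.82 |
| 4 | 224 d = 7.36 | 28 d = 0.92 | 6.44 |
| 8 | 196 d = 6.44 | 56 d = 1.84 | 4.60 |
| 12 | 168 d = 5.52 | 84 d = 2.76 | 2.76 |

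The error is zero only where 36 − 2w = 0, at w = 18.

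**Examples.**

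- Chronological age 6.0 months, 4 weeks early: the SAP gives 6.0 − 7.36 = −1.36 months; the intended value is 6.0 − 0.92 = 5.08.
- Chronological age 8.0 months: w = 4 gives 0.64 (should be 7.08), w = 8 gives 1.56 (6.16), and w = 12 gives 2.48 (5.24).

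**Ages below the lowest category.** Computed age is below 1 month until chronological age reaches 1 plus the SAP deduction: 8.4 months at w = 4, 7.4 at w = 8 and 6.5 at w = 12.

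**Reaching the 6-month boundary.** The largest computed age before 12 months is 12 minus the SAP deduction: 4.64 at w = 4, 5.56 at w = 8 and 6.48 at w = 12. An infant must be about 10 or more weeks early to be placed at 6 months or above at all.

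**Regrouping.** Take infants under 12 months whose properly corrected age is at least 6 months, with ages spread evenly (an assumption).

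- w = 4: chronological ages 6.92 to 12, a span of 5.08 months. Those below 8.36 are computed as under 1 month: (8.36 − 6.92)/5.08 = 28%. The other 72% move to 1 to <6 months.
- w = 8: computed ages run from 1.40 to 5.56, so all move to 1 to <6 months.
- w = 12: chronological ages 8.76 to 12, a span of 3.24. Only those from 11.52 stay: 0.48/3.24 = 15%. The other 85% move.

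Over all infants under 12 months with properly corrected age of at least 1 month, the share left in the right group is 0% at w = 4, 4% at w = 8 and 33% at w = 12.

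**PK normalisation.** An infant wrongly moved below 6 months has the concentration scaled to 7 rather than 10 mg/kg, so the normalised value is 7/10 of what it should be.

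**Field holding gestational age g instead.** The deduction is (36 − g) × 7/30.4375: 2.76 months at 24 weeks, 0.92 at 32, 0 at 36 and −0.92 at 40. This is sensible for pre-term infants, but an infant born at 40 weeks is made 0.92 months older.

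**The case against.** The strongest defence is that the constant 36 suggests a gestational-week input. If the CRF field holds gestational age at birth, the pre-term deductions are workable and the 2.8 to 7.8 month error disappears. The CRF is not in the documents, so this cannot be excluded. However, it contradicts the label in both SAP sections that name the field. The size of the error therefore depends on the reading; the need for correction does not.

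On scope, the opening sentence of SAP 3.2.5.2 speaks of pre-term birth, the weeks are listed only after a yes, and SAP section 1 defers to the protocol unless the SAP specifies otherwise. Together these suggest that term infants were not meant to be corrected, and the recorded-0 case may never occur. That supports calling the second fault a missing condition. But the rule as written specifies every subject under 12 months, and a program follows the rule.

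The reach is also limited:

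- The overall primary test on FAS_A does not use age.
- The primary age table pools 1 month to <1 year, so only computed ages below 1 month matter there.
- By-visit secondary efficacy and TEAE summaries combine the age groups.
- Limits that change at 12 months are unaffected.
- The number of pre-term infants is not given, and SAP 3.1 expects few subjects in the two youngest groups.

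All of this stands. Negative ages would probably be noticed in the demographics listing, but a value such as 1.56 months for an 8-month-old might not be, and noticing it does not supply the right formula.

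**Conclusion.** The concern holds. Formula and label cannot both be right, no other section gives a usable definition, and the rule omits the protocol's restriction to pre-term infants. The size quoted is conditional on the field holding weeks early and on the assumed range of w; the regrouping shares also assume evenly spread ages.

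The number of infants affected is unknown, but Protocol 5.1.5 plans at least 5 subjects in each of the two age groups under 1 year, so the unrestricted rule applies to at least 10 planned subjects. In groups that small, one misplaced infant matters. The confirmatory conclusion is not at risk. The correction is still essential, because the default age variable cannot be programmed from this text without an undocumented choice.

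**What to change.** 1. Confirm what the CRF field holds and state it in SAP 3.2.5.2.
2. Apply the correction only to subjects recorded as pre-term with chronological age under 12 months. Use chronological age for everyone else.
3. If the field is weeks early, deduct weeks × 7 days. If it is gestational age at birth, rename it, state the term reference week, and deduct (reference − gestational age) × 7 days.
4. Re-derive age at entry, the age categories, the PK grouping and normalisation reference, and the age-dependent safety limits.

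Do not hard-code weeks × 7 before step 1: if the field holds gestational age, an infant born at 32 weeks would lose 32 × 7 = 224 days.

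The cost is one CRF check, one revised definition and a change to the derivation program. No new data are needed.
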